4 SELECTION AND ENROLLMENT OF STUDY SITES AND PATIENTS

Patients will be included in this study if they are veteran organ transplant recipients that receive immunosuppressant medications through the VA system. Organ transplant recipients will be identified using ICD-9/10 codes from the VA electronic health record (CPRS), with this data housed in the CDW. Once identified, active medications will be queried and those receiving immunosuppressant medications to prevent rejection (tacrolimus, cyclosporine, azathioprine, mycophenolate, sirolimus, everolimus, or belatacept) will be included in the study. There are no exclusion criteria for patients in this study as recruitment is at the VA site-level. As this is a cluster-randomized study and randomization will occur at the site level and not the patient-level, participants will not be recruited for the study, and data collection will occur through querying and linking the VA CDW, the SRTR transplant registry and CMS data repositories. We will request waiver of written documentation of patient informed consent. We will also request HIPAA authorization waiver as well for all patients. The following protected health information (PHI) elements will be required to complete the study with the HIPAA authorization waiver.

| PHI Required for Study | Rationale |
|--|---|
| Social Security Number | Require real SSNs to create finder file and send to Scientific Registry of Transplant Recipients (SRTR) to acquire baseline transplant information and graft outcomes |
| Date of transplant, date of clinical events (including graft loss, rejections, | Require dates to ensure events occurred during the study period and to conduct |

| | |
|--|--|
| hospitalizations, emergency department visits and death) | time to event survival analyses for primary and secondary aims |
| Zip codes | Require zip code to assess and adjust for potential geographic confounding in multivariable analyses |

4.1 Inclusion Criteria (require both to be included)

- Veteran organ transplant recipients will be identified using ICD-9/10 codes from the VA electronic health record (CPRS). Patients must have an active code stating they are a recipient of an organ transplant. The following codes will be utilized:
 - ICD-9 codes: V42.0, V42.1, V42.6, V42.7, V42.83, V42.84, 996.81, 996.82, 996.83, 996.84, 996.86, 52.80

OR

- ICD-10 codes: C80.2, T86.1, T86.10, T86.11, T86.12, T86.13, T86.19, T86.2, T86.20, T86.21, T86.22, T86.23, T86.290, T86.298, T86.3, T86.30, T86.31, T86.32, T86.33, T86.39, T86.4, T86.40, T86.41, T86.42, T86.43, T86.49, T86.810, T86.811, T86.812, T86.818, T86.819, T86.9, Z48.2, Z48.21, Z48.22, Z48.23, Z48.24, Z48.280, Z48.288, Z48.298, Z94.0, Z94.1, Z94.2, Z94.3, Z94.4, Z94.83

AND

- Actively receiving at least one anti-rejection medication dispensed by the VA site. These medications include tacrolimus, cyclosporine, azathioprine, mycophenolate, sirolimus, everolimus, and belatacept.

4.2 Exclusion Criteria

- There are no exclusion criteria for patients in this study as recruitment is at the level of the VA site.
- All veterans meeting inclusion criteria will be monitored by the dashboard system and will be included in the outcomes assessment. Patients may enter or exit the study in a rolling manner, which will be accounted for during analyses.

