| Hemoglobin A1C | >8% | >20% Increase |
| Low Density Lipoprotein (LDL) | >190 mg/dL | >30% Increase |
| Triglycerides (TG) | >500 mg/dL | >30% Increase |
| Tacrolimus (FK) Trough | <3 or >15 ng/mL | >20% Change |
| Cyclosporine (CyA) Trough | <30 or >400 ng/mL | >20% Change |
| Sirolimus (Rapa) Trough | <2 or >8 ng/mL | >20% Change |
| Everolimus (RAD) Trough | <2 or >8 ng/mL | >20% Change |
| Interacting Drugs | | Trigger Definitions |
| Enzyme Inhibitors – INPATIENT OR OUTPATIENT | | |
| Macrolides (clarithromycin, erythromycin, telithromycin) | | |
| Azoles (ketoconazole, itraconazole, voriconazole, posaconazole, fluconazole, isavuconazole) | | |
| Calcium Channel Blockers (diltiazem, verapamil) | | |
| HIV (nafazodone, delavirdine, saquinavir, nelfinavir, indinavir, amprenavir) | | |
| Miscellaneous (boceprevir, telaprevir, cimetidine, chloramphenicol, danazol) | | |
| Enzyme Inducers - INPATIENT OR OUTPATIENT | | |
| Antiepileptics (carbamazepine, phenytoin, phenobarbital) | | |
| Rifamycins (rifampin, rifabutin) | | |
| Miscellaneous (St. John's Wort, neviripine, efavirenz, enzalutamide) | | |
| Other | | |
| atorvastatin >10mg, rosuvastatin >10 mg, simvastatin >10 mg with Cyclosporine ONLY | | Initiation Discontinuation Dose Change >20% |
| Encounters | | Trigger Definition |
| Hospitalization or ED visit | | At discharge |
| Immunosuppression | | Trigger Definition |
| Tacrolimus, cyclosporine, mycophenolate, azathioprine, sirolimus, everolimus, prednisone | | PDC <80%, late refill (10 days), drug expired |

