5.3 Usual Care

Both the control and intervention groups will continue to receive usual care as part of this study. Patients at the control sites will receive standard of care, and patients at the intervention sites will receive standard of care plus the pharmacist-led intervention. Usual care for Veteran organ transplant recipients across the 10 study sites varies somewhat, but generally includes the following: at most sites, nurse coordinators and/or mid-level practitioners are responsible for general transplant patient oversight, including ensuring laboratory assessments are scheduled/reviewed and medication regimens are accurate and up to date. However, large patient numbers and workload constraints preclude these health care professionals from prospective detailed daily monitoring of patients. If there is non-adherence to laboratory assessments or medications, they are rarely identified concurrently or early after they occur. Thus, medication safety issues that arise usually do not get identified or addressed until they have caused a clinically significant issue, leading to a health care encounter (clinic visit, ER visit, hospitalization). In addition, during this long-term ambulatory phase of care for transplant patients, pharmacists usually act as consultants and are only involved in direct patient care if an issue arises, and the nurse or provider engages the pharmacist for assistance. Within usual follow up care, pharmacists do not conduct routine daily surveillance of all transplant patients. Most transplant patients have multiple physician providers, both within and outside the VA system, providing care and medication management. This includes a primary care physician to manage common comorbidities (hypertension, diabetes, etc.) and a specialist (nephrology, hepatology) to manage allograft function; other specialists, including endocrinologists and cardiologists, are commonly involved with this patient population as well. Thus, care coordination and communication across these providers and health care organizations can often be fragmented. This usual care environment is complex and difficult to navigate, even for patients with high health literacy.^{3,18}

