9.4 Data Analyses

The data analysis will incorporate the intent-to-treat principle; namely, all participants enrolled in the intervention group will be included in the analysis and compared to all of the patients captured within the control group. If a patient dies, has graft loss or moves out of their study site, their data will be censored at that time point. For comparative statistical assessments within the utilization outcomes, the two groups will be compared using a generalized linear mixed models (GLMM) approach.⁵⁴ This approach allows for measurement of participants at different time points, clustering by study site, missing data under the assumption of missing at random (MAR), time varying or invariant covariates, and can also account for the effect of correlated longitudinal measurements within participants. In addition, GLMM accommodates a wide range of distributional assumptions such as dichotomous (e.g. binomial), count (e.g. Poisson), continuous

(e.g. Gaussian), and categorical or ordinal outcomes. For comparing the primary outcome (ED visit and hospitalization rates), we will use GLMM (with appropriate link function) with counts of these events as the outcome variable and intervention group (yes/no) as the primary independent variable. This analysis is equivalent to Poisson regression or negative binomial regression (in the case of over-dispersion), both special cases of GLMM. Additional adjustment covariables will be added to the model in a second set of analyses. Covariates will include patient sociodemographics: age, sex, race, comorbidities (using modified Elixhauser definitions), marital status and education. In these models, donor information (age, sex, race, deceased or living) and transplant characteristics (HLA mismatches, ischemic times, panel reactive antibody levels, time since transplant) will also be included. This will assist in making valid intervention effect estimates after accounting for baseline differences, as there may be patient-level differences between groups. The magnitude of between intervention differences on outcome variables (effect sizes) at each time point will be estimated using appropriate contrasts in the corresponding GLMM models.

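### The primary population stays open after site randomisation and is keyed to VA dispensing, which the intervention acts on, with no cohort date and no rule for late entry or lapsed dispensing

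*Combined protocol and SAP*

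**What the plan says.** - Section 4.1 requires a transplant code and, in addition, "Actively receiving at least one anti-rejection medication dispensed by the VA site". It gives no date at which this is tested and no look-back window that defines active receipt.
- Section 4.2 includes everyone who qualifies: "All veterans meeting inclusion criteria will be monitored by the dashboard system and will be included in the outcomes assessment". It then adds: "Patients may enter or exit the study in a rolling manner, which will be accounted for during analyses".
- The monitoring table in Section 5.1 lists the dashboard triggers for immunosuppressants as "PDC <80%, late refill (10 days), drug expired". The pharmacist then works to resolve the non-adherence.
- Section 5.3 says of missed laboratory work or medication under usual care that "they are rarely identified concurrently or early after they occur".
- Section 9.4 states: "The data analysis will incorporate the intent-to-treat principle". Its only written rule for ending follow-up is: "If a patient dies, has graft loss or moves out of their study site, their data will be censored at that time point". The primary model is a generalised linear mixed model on event counts with arm as the main predictor. No offset for time at risk, no handling of late entrants and no rule for lapsed dispensing appears there.

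**The concern.** In a cluster trial without patient enrolment, the analysis set is whatever the data query returns. Here the query depends partly on VA dispensing after randomisation, and dispensing is one of the things the intervention is built to change. If membership follows current dispensing, treatment can alter who is counted in each arm. An offset would correct for how long patients are observed, but not for which patients are observed.

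The patients concerned are unlikely to be average. Section 2.1 cites non-adherence in 32% of kidney recipients with graft failure against 3% of those without. Suppose their high-risk time were lost at control sites and kept at intervention sites. The primary rate ratio would then be pulled towards or above 1, and a real benefit could be missed. The missing-at-random assumption in Section 9.4 would not protect against this unless the model captured what drives exit.

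The plan also lets two analysts build different cohorts from the same data. That choice should be closed before outcomes are seen.

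**Working it through.** **1. The plan's own sample size.** Inputs from Section 9.2: control rate 1.269 per person-year, 25% reduction (0.952), ICC 0.05, 80% power, two-sided alpha 0.05, 10 sites. Follow-up is 2 years.

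- Per arm, n = (1.960 + 0.842)² × (1.269 + 0.952) / [2 × (1.269 − 0.952)²] ≈ 86.6, or 173 in total.
- Design effect with 1,350/10 = 135 per site: 1 + 134 × 0.05 = 7.7.
- 173 × 7.7 ≈ 1,334, close to the stated 1,350.
- Allowing for 15% loss: 1,350/0.85 ≈ 1,589, consistent with the stated 1,600.

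The figure reproduces and is not in question.

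**2. Does a lapse end follow-up?** The passages point in different directions.

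- *Permitting it:* Section 4.1 makes active dispensing a condition of eligibility, and Section 4.2 allows exit. Section 4.3 says that patients are not enrolled individually, so any exit must be read from records. Moving out of the study site has no data definition. Section 2.2 reports that nearly two-thirds of veteran recipients are dual users, so a lapse, a move and a switch to non-VA supply may look alike.
- *Against it:* lapse is not among the censoring events in Section 9.4. The expired-drug trigger presupposes that the patient is still monitored. Section 9.3.2 compares mean adherence across all patients in both arms each month. Section 4.1 needs only one of seven drugs.

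The text therefore permits exit on lapse but does not state it.

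**3. Entry.** Patients who qualify after randomisation are included in the primary comparison under Section 4.2. Both arms use the same automated query, so this route is weaker than exit.

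**4. Possible size.** The documents give no lapse rates, so every input here is an assumption. Let p be the share of person-time spent lapsed, R the event rate in that time relative to other time, and f the fraction of it lost from an arm's cohort. The observed rate in an arm is proportional to

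[(1 − p) + p(1 − f)R] / [(1 − p) + p(1 − f)],

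and the apparent null ratio is intervention over control.

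- *Small case:* 10% of patients lapse for 3 of 24 months, so p = 0.10 × 3/24 = 0.0125. Take R = 2, with all lapsed time lost in control (observed rate 1) and half lost in intervention. The ratio is (0.9875 + 0.0125)/(0.9875 + 0.00625) = 1.006. A true 0.75 reads 0.755.
- *Middle case:* p = 0.10, R = 2, 50% lost in control, 10% in intervention. Intervention: (0.90 + 0.18)/(0.90 + 0.09) = 1.091. Control: (0.90 + 0.10)/(0.90 + 0.05) = 1.053. The ratio is 1.036, and 0.75 reads 0.777.
- *Upper case:* p = 0.20, R = 3, 80% lost in control, 20% in intervention. (1.28/0.96)/(0.92/0.84) = 1.217, and 0.75 reads 0.913.
- *Lapse never ends follow-up:* f = 0 in both arms and the ratio is exactly 1.

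By the method of step 1 with 1,436 patients, power is 0.81 with no bias, 0.71 in the middle case and 0.15 in the upper case.

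**5. Size with a closed cohort.** 1,689 × 0.85 ≈ 1,436, above 1,350. Power by the same method is 0.808.

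**The case against.** The strongest reply is that exit on lapse is an inference. The written censoring events are death, graft loss and moving from the site. The adherence alerts and the all-patient adherence comparison make most sense if lapsed patients stay in. Events come from VA records and linked Medicare claims (Section 9.3.1), so capture does not depend on dispensing. An open cohort is also a legitimate choice for population surveillance, and analysing captured patients by their site's arm is not in itself a breach of intent-to-treat.

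Much of this stands. A reader might infer that lapsing control patients do leave the analysis while intervention patients are kept. The documents do not say so. A reader might also infer that the intervention adds newly identified low-risk patients and so biases in its own favour. No passage supplies that mechanism: identification is by code and active-medication query in both arms, and the dashboard covers patients who already qualify.

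What the reply does not answer is that Section 4.2 promises handling that Section 9.4 omits. Leaving the site is undefined in the data, and post-randomisation entrants sit in the primary comparison.

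**Conclusion.** The concern holds as an avoidable exposure to post-randomisation selection, not as a demonstrated bias. The primary population is open after randomisation and tied to a variable the intervention acts on. The rules that would keep the arms' cohorts comparable are not written.

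The size is not determined by the documents. It is zero if lapse never ends follow-up, about 1.006 on the null ratio in the small case, and up to 1.217 under the strongest assumptions tried. Where exit on lapse occurs, the likely direction is against the intervention. That assumes lapsed time carries more events and that more of it is lost in the control arm.

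A reader might equate a share of patients who lapse (say 5–15%) with the same share of person-time. With half kept only in the intervention arm and R from 1.5 to 3, the null ratio would then read 1.01–1.16. That is too strong, because it removes every lapsing control patient for the full 24 months, including time before the lapse.

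**What to change.** In Sections 4.2 and 9.4:

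- Define the primary analysis set as all patients meeting Section 4.1 in the VA data warehouse on one date common to all sites, either randomisation or go-live. Use the same stated look-back window for active dispensing in both arms.
- Analyse these patients by their site's arm for 24 months, with a log person-time offset.
- State that a lapse in VA dispensing neither ends follow-up nor counts as moving from the site, and define moving from the site in data terms.
- Analyse later entrants, and any dispensing-based exit, only as a sensitivity analysis.

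This fits the 24-month monitoring in Section 9.1 and uses data sources already planned. The cost is SAP wording and one extract date. The downside is that later entrants leave the primary analysis. The planned size is kept only if the 1,689 are patients active on the chosen date, which Section 9.2 does not say. The margin over the required 1,600 is 89, so the sponsor should confirm this. The change does not address the explicit censoring at death and graft loss, which the intervention may also affect.

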4.3 Study Enrollment Procedures

Once IRB approval is obtained (via central IRB), each potential participating pharmacist will undergo informed written consent. Following this, each site will be randomized to

standard care or standard care plus the pharmacist-led intervention. To ensure a roughly equal number of patients between the two comparison groups, randomization will be stratified by estimates veteran organ transplant recipients (<125 versus ≥ 125 active patients). After randomization, each participating pharmacist will be informed of their assigned group. Those in the intervention arm will be trained on the dashboard system, utilizing the dashboard, and delivering the intervention. Those in the usual care group will continue to provide the same level of care they are currently providing as part of their normal day-to-day activities and job functions.

If a site or participating pharmacist withdraws prior to study initiation, if possible, it will be replaced with a suitable alternative site/pharmacist. If a site pharmacist withdraws after initiation, the investigational team will determine if the site needs to be replaced. This will depend on how far along the intervention is and the number of veterans impacted by the withdrawal.

Because this is a cluster-randomized trial, and randomization occurs at the site level, we will not recruit, consent, or enroll at the subject level. We will request waiver of written documentation of patient informed consent. We request waiver of HIPAA for all patients.

5 STUDY INTERVENTIONS

5.1 Interventions

The sites randomized to the intervention arm will continue to use current standard of care procedures within their sites (described below), while also utilizing the dashboard system daily to identify Veteran transplant recipients with potential medication safety issues. Each day, the pharmacists will open the dashboard system, which is updated each morning. The system will identify new patient-specific alerts that will inform the pharmacist on potential medication safety issues. The pharmacist will then serve as a patient navigator, intervening to resolve the medication safety issue, by using protocols embedded within the SOP manual that the pharmacists will be trained on prior to study initiation. Once the pharmacist validates that the dashboard alert is a relevant issue, they will develop a management plan using these protocols, discuss the recommendations with the providers (when necessary), agree on a plan, and implement the plan.

The four primary medication safety issues the intervention pharmacists will be alerted to and address are laboratory abnormalities, medication non-adherence, drug interactions and medication coordination/communication issues. For laboratory abnormalities, common issues encountered within transplant patients include electrolyte irregularities, organ dysfunction, drug level outliers and cytopenias. For each of the laboratory values that will be monitored and reported in the dashboard, a detailed algorithm will be provided delineating how to address the issue, within the SOP manual (see below). As one example, it is well known that magnesium levels are low in transplant recipients due to a side effect of calcineurin inhibitors.⁵⁰ Strategies to address this include dietary interventions and supplementation. Issues with out-of-range drug levels will also be

addressed. These include ensuring the patient is taking the correct dose, ensuring the level is a true trough value, checking for new drug interactions and adjusting the dose when necessary. When medication non-adherence is identified as a potential issue, the pharmacist will determine if it is deliberate or unintentional. Strategies to address deliberate non-adherence include removing perceived or actual barriers, using motivational interviewing, and addressing side effects and cost issues. For unintentional non-adherence, pharmacists can implement trigger reminder strategies, simplify regimens, and re-educate. Within drug-interaction alerts, the intervention will focus on reducing the impact of these through changing of regimens (when appropriate), educating patients and/or providers and increased monitoring and surveillance.⁵¹ Alerts for medication coordination issues will encompass discharges from the ER and hospital and missed laboratory assessments. The intervention pharmacist will ensure accurate and safe medication regimens through medication reconciliation and improved medication safety surveillance through the scheduling and follow up of laboratory assessments.¹⁷

To ensure fidelity across sites and efficiency for providers, the specific day-to-day tasks involved with this intervention, which include assessing and intervening on the alerts and appropriate follow up with patient and providers, are fully developed and incorporated within the SOP manual. This manual was vetted by transplant clinicians, provided to each intervention site pharmacist, with appropriate training.

| Monitoring Variable | Absolute Value Thresholds | Trajectory Threshold |
|---|---------------------------|---|
| Laboratory Assessments – ONLY OUTPATIENT | | |
| Potassium (K) | <3 or >5.5 mEq/L | >30% Change |
| Bicarbonate (CO2) | <18 or >30 mEq/L | >30% Change |
| Blood Urea Nitrogen (BUN) | >40 mg/dL | >30% Increase |
| Creatinine (Cr) | >2.5 mg/dL | >20% Change |
| Glucose (Gluc) | <60 or >300 mg/dL | >30% Change |
| Calcium (Ca) | <7 or >10 mg/dL | >30% Change |
| Magnesium (Mg) | <1.0 or >2.5 mEq/L | >30% Change |
| Phosphorus (PO4) | <2.0 or >5.0 mg/dL | >30% Change |
| White Blood Cell (WBC) Count | <3.0 or >15.0 cells/mm3 | >30% Change |
| Hemoglobin (Hgb) | <8 or >15 gm/dL | >20% Change |
| Platelets (Plt) | <50 or >500 cells/mm3 | >30% Change |
| Alanine Aminotransferase (ALT) | >160 U/L | >30% Increase |
| Total Bilirubin (T Bili) | >1.5 mg/dL | >20% Increase |
| Hemoglobin A1C | >8% | >20% Increase |
| Low Density Lipoprotein (LDL) | >190 mg/dL | >30% Increase |
| Triglycerides (TG) | >500 mg/dL | >30% Increase |
| Tacrolimus (FK) Trough | <3 or >15 ng/mL | >20% Change |
| Cyclosporine (CyA) Trough | <30 or >400 ng/mL | >20% Change |
| Sirolimus (Rapa) Trough | <2 or >8 ng/mL | >20% Change |
| Everolimus (RAD) Trough | <2 or >8 ng/mL | >20% Change |
| Interacting Drugs | | Trigger Definitions |
| Enzyme Inhibitors – INPATIENT OR OUTPATIENT | | |
| Macrolides (clarithromycin, erythromycin, telithromycin) | | |
| Azoles (ketoconazole, itraconazole, voriconazole, posaconazole, fluconazole, isavuconazole) | | |
| Calcium Channel Blockers (diltiazem, verapamil) | | |
| HIV (nafazodone, delavirdine, saquinavir, nelfinavir, indinavir, amprenavir) | | |
| Miscellaneous (boceprevir, telaprevir, cimetidine, chloramphenicol, danazol) | | |
| Enzyme Inducers - INPATIENT OR OUTPATIENT | | |
| Antiepileptics (carbamazepine, phenytoin, phenobarbital) | | |
| Rifamycins (rifampin, rifabutin) | | |
| Miscellaneous (St. John's Wort, neviripine, efavirenz, enzalutamide) | | |
| Other | | |
| atorvastatin >10mg, rosuvastatin >10 mg, simvastatin >10 mg with Cyclosporine ONLY | | Initiation Discontinuation Dose Change >20% |
| Encounters | | Trigger Definition |
| Hospitalization or ED visit | | At discharge |
| Immunosuppression | | Trigger Definition |
| Tacrolimus, cyclosporine, mycophenolate, azathioprine, sirolimus, everolimus, prednisone | | PDC <80%, late refill (10 days), drug expired |

